#### 5.4.2 Key secondary analysis

Not applicable.

#### 5.4.3 Secondary analysis

Binary variables will be analyzed using the logistic model; code is described above ([Section 5.4.1](#)).

For continuous secondary XXXXXXXXXX efficacy variables, MMRM approach will be used with treatment, visit, and TNF-alpha inhibitor status as factors, Week 16 score and Week 16 weight as covariates, and treatment-by-visit and Week 16 score-by-visit as interaction terms.

The following SAS code will be applied :

```
Proc mixed data=<dataset> order=internal method = reml;
class visit TNF-alpha ;
model Change_score = Wk16_score TNF-alpha Wk16_weight avisit trt*avisit
Wk16_score*avisit / s ddfm=kr;
repeated visit / type=un subject=USUBJID;
lsmeans visit / cl;

run;
where;
Wk16_score = Week 16 score
avisit = Analysis visit (Week 20, 24,28, 32, 36, 40, 44, 48 and 52)
TNF-alpha = TNF-alpha status
weight = subject weight
USUBJID= Subject ID
Change_score = Change in score of specified variable from Week 16 to each post-
baseline visit
```

In case the MMRM model does not converge the following sequential steps will be used:

1. change ddfm=kr to ddfm=bw. If still no convergence, perform step 2.
2. change type=un to type=cs. If still no convergence, perform step 3.
3. remove covariates in the following order until convergence is achieved: weight, blscore\*visit, TNF-alpha.

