#### Change from Week 16 in total BASDAI

Analysis of change from Week 16 in total BASDAI score will be performed using mixed-effects model repeated measures (MMRM) with treatment, visit, and TNF-alpha inhibitor status (naive, inadequate responder) as factors, Week 16 score and Week 16 weight as covariates, and treatment-by-visit and Week 16-by-visit as interaction terms (Diggle, Heagerty, and Liang KY, 2002). The least-squares (LS) mean difference between secukinumab 150 mg - 300mg (IR) and secukinumab 150 mg - 150mg (IR) will be presented along with the corresponding 95% CI.

Similar analysis will be performed for the subgroups defined by TNF-alpha inhibitor status.

Descriptive summary statistics for change from baseline in Treatment Period 1 and change from Week 16 in Treatment Period 2, for total BASDAI score for each visit will be provided. Similarly, descriptive summary statistics will also be provided by TNF-alpha inhibitor status.

Analysis of change from Week 16 in **ASAS-Health Index** and change from Week 16 in **FACIT-Fatigue** will be similar to analyses as described for change from Week 16 in total BASDAI.

Analysis of **BASDAI50 response**, **ASAS20 response**, **ASAS40 response**, and **ASAS partial remission** will be similar to the analyses as described for reduction in ASDAS  $\geq 1.1$  from Week 16.

Also summary statistics for secondary efficacy variables 1, 2, 4 and 5 for the patients in Treatment Period 1 who entered Treatment Period 2 will be provided based on the below criteria :

- Patients receiving 150mg (open label) (Enrolled Set)
- Patients receiving randomized 300mg and 150mg (Randomized Set)

- Patients who are responders (Responder Set)
- Patients who are nonresponders (Nonresponder Set)

In addition, the above analysis will be done by TNF-alpha inhibitor status and by visit.

As additional analyses, following will be performed on Full Analysis Set:

1. Descriptive summary statistics for change from baseline (Week 0) to all visits in Treatment Period 2 for secondary efficacy variables - total BASDAI, ASAS-Health Index and FACIT-Fatigue, will be provided.
2. Number and percentages of patients for secondary efficacy variables 3 - 6 will also be reported for each treatment group considering baseline (Week 0) to derive the response for Treatment Period 2 and similarly by TNF-alpha inhibitor status only for ASAS20 and ASAS40 response.

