### **2.7.3 Handling of missing values/censoring/discontinuations**

For secondary efficacy variables 1 and 3 – 6, patients who discontinue prematurely for any reason will be considered nonresponders from the time they discontinued through to Week 52. Also, patients who do not have the required data to compute response (e.g., ASAS components) at the specific time point will be classified as nonresponders.

Secondary efficacy variables 2, 7, and 8, will be analyzed using a mixed-effects model repeated measures (MMRM) which is valid under the missing at random (MAR) assumption. For analyses of these variables, if all post-baseline values are missing then these missing values will not be imputed and the patient will be removed from the analysis of the corresponding variable, i.e., it may be that the number of patients providing data to an analysis is smaller than the number of patients in the FAS.

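### The MMRM non-convergence ladder opens with a step that cannot restore convergence, then drops straight to compound symmetry with model-based errors, which can make the Week 52 interval too narrow

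*SAP*

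**What the plan says.** SAP 2.7.2 analyses change from Week 16 in total BASDAI by MMRM and reports the least-squares mean difference with its 95% interval. ASAS-HI and FACIT-Fatigue follow the same plan. For the TNF strata it adds: "Similar analysis will be performed for the subgroups defined by TNF-alpha inhibitor status". SAP 2.7.3 describes the method as a "mixed-effects model repeated measures (MMRM) which is valid under the missing at random (MAR) assumption".

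The code is in SAP 5.4.3. The call is "Proc mixed data=<dataset> order=internal method = reml", with no option for empirical standard errors. The covariance is set by "repeated visit / type=un subject=USUBJID", and the visits are listed as "Analysis visit (Week 20, 24,28, 32, 36, 40, 44, 48 and 52". Degrees of freedom are Kenward-Roger.

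For non-convergence the SAP gives three sequential steps. The first moves from Kenward-Roger to between-within degrees of freedom: "change ddfm=kr to ddfm=bw. If still no convergence, perform step 2". The second, which replaces the unstructured matrix by compound symmetry, reads "change type=un to type=cs. If still no convergence, perform step 3". The third takes terms out of the model one at a time: body weight, then the interaction of the starting score with visit, then TNF status.

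The ladder names no structure between unstructured and compound symmetry, never returns to Kenward-Roger, and does not call for sandwich errors at any step.

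**The concern.** There are two separate problems.

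**Step 1 does not address non-convergence.** The `ddfm` option sets the denominator degrees of freedom and, for Kenward-Roger, a standard-error adjustment, after the REML optimisation has finished. It is not part of the likelihood. A covariance fit that fails under `kr` fails in the same way under `bw`. Because the steps are sequential, the small-sample correction is already gone when step 2 is reached.

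**Step 2 goes from the most flexible structure to a very restrictive one.** Compound symmetry forces one residual variance on all nine visits and one correlation on all pairs. The outcome is change from Week 16, and the model adjusts for the Week 16 score and its interaction with visit. If correlation with Week 16 fades over 36 weeks, that adjustment removes more variance at Week 20 than at Week 52. The common variance then understates the variance at Week 52, which is the time point of all three continuous secondary objectives.

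This is an estimation trial, so the interval is the result that readers will use. If the fallback is reached, its coverage depends on an assumption that the plan does not protect against.

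**Working it through.** **The plan's own figures.** The SAP states none for the ladder. Its sample size (SAP section 3) reproduces: n per arm = 1.96² × (0.2×0.8 + 0.1×0.9) / 0.10² = 96.04, rounded up to 97. Also 270 × 0.9 × 0.8 = 194.4, matching the 194 to be randomised.

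**Covariance parameters.** Nine visits give 9 × 10 / 2 = 45 under unstructured and 2 under compound symmetry.

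**Step 1.** The two-sided 95% critical value is 1.973 at 185 df and 1.962 at 1500 df, a change of under 1%. For a 78-patient subgroup, with 70 and 600 df assumed, it is 1.994 and 1.964, about 1.5%.

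**Step 2, complete data.** The compound-symmetry standard error at Week 52, relative to the true one, is

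ratio = √(mean residual variance over the nine visits / residual variance at Week 52),

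and coverage = 2Φ(1.96 × ratio) − 1.

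The documents give no SDs, visit correlations or Treatment Period 2 dropout rate, so every pattern below is an assumption. Let ρ(d) be the correlation between the Week 16 score and the score d visits later. With unit raw variance, the residual variance at visit d is 1 − ρ(d)². For ρ = 0.9^d, the mean over d = 1 to 9 is 0.597 and the Week 52 value is 0.850. The ratio is √(0.597/0.850) = 0.838 and coverage is 90.0%.

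| Assumed pattern, complete data | Ratio | Coverage |
|---|---|---|
| 0.8 × 0.98^d | 0.924 | 93.0% |
| 0.8 × 0.95^d | 0.899 | 92.2% |
| 0.9^d | 0.838 | 90.0% |
| 0.95^d | 0.794 | 88.0% |
| 0.95^d, raw variance rising 30% by Week 52 | 0.764 | 86.6% |
| AR(1) 0.9 to 0.95 with 30% to 50% measurement noise | 0.930 to 0.967 | 93.2% to 94.2% |
| Constant residual variance, any correlation | 1.000 | 95.0% |

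In 4,000 simulated trials at 39 per arm with complete data, compound symmetry covered 91.9% under 0.8 × 0.95^d and 89.8% under 0.9^d. Visit-specific variances covered 95.0% and 95.4%.

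**Step 2 with dropout** (completely at random, 97 per arm):

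- Constant variance, AR(1) 0.8 to 0.95, 15% to 25% dropout: 93.7% to 94.5%.
- Residual SD rising 20%, 50% or 100% from Week 20 to Week 52, lag-one correlation 0.9, 25% dropout: 91.2%, 88.0% and 84.0%.
- Residual SD falling 20%, 25% dropout: ratio 1.07 to 1.14, coverage 96.4% to 97.4%, so the interval is too wide.

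Sandwich errors returned 95% in each of these dropout settings, as a large-sample result.

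**Where the fallback might be reached.** SAP 1.1 caps TNF-IR patients at 40% of enrolment. If 40% of those randomised are TNF-IR, that is 0.40 × 194 ≈ 78, or about 39 per arm. This is an expectation and not a ceiling. The cap allows 0.40 × 270 = 108 enrolled, about 97 after 10% open-label discontinuation, and so up to about 49 per arm if all of them were inadequate responders.

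**The case against.** The strongest reply is that the fallback may never be used. The unstructured matrix is pooled over both arms, so 78 patients supply up to 78 × 9 = 702 observations for its 45 parameters. Setting 39 per arm against 45 parameters therefore overstates the difficulty. In simulated data with monotone dropout, a nine-visit unstructured REML fit converged in all 60 runs of every setting tried: 194 patients (25% dropout), 78 (15%, 25% and 40%) and 50 (25%). That used Fisher scoring and assumed covariances, not PROC MIXED's own optimiser. Even so, it gives no sign that the fallback would normally be reached. This stands, and it limits the weight of the point.

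A reader might also infer that the ladder necessarily makes the Week 52 interval too narrow. The documents do not support that. They contain nothing on SDs or correlations, and the same rule gives correct coverage with constant variance and complete data, and over-coverage if variance falls. Narrowing is the likelier direction, because adjusting for Week 16 usually leaves residual variance that grows with time, but that is a judgement.

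The loss from step 1 is small, and the stakes are limited to secondary variables 2, 7 and 8, none of them designated a key secondary endpoint. Both remarks are fair. They do not rescue a first step that does nothing for convergence, or explain why every intermediate structure is skipped.

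**Conclusion.** The point holds in conditional form. That step 1 cannot restore convergence is a property of the method and needs no assumption; its cost is about 1% to 1.5% in the critical value. That step 2 can under-cover at Week 52 rests on two conditions that the documents do not establish: that the fallback is triggered, and that residual variance grows towards Week 52 (decaying correlation combined with dropout has a smaller effect). Where both hold, coverage is about 87% to 93% under the assumed decaying correlations with complete data. It is closer to nominal with substantial measurement noise, and reached 84% in the worst dropout scenario tried.

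The main 194-patient analyses will probably not be touched; the TNF-IR subgroup is the most plausible place for it to matter. The primary logistic regression is unaffected. This is a cheap improvement to a contingency rule, not a defect in the trial's main result.

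**What to change.** Replace the first two steps of the ladder in SAP 5.4.3:

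- Delete step 1. Keep `ddfm=kr` with `type=un` as the base model.
- On non-convergence, try heterogeneous structures in one fixed order, for example TOEPH, then ARH(1), then CSH, each with `ddfm=kr`. Other orders are defensible; what matters is that the order is set in advance.
- Use homogeneous compound symmetry only as the last covariance step, with empirical (sandwich) standard errors and a stated compatible degrees-of-freedom method, for example `ddfm=bw`.
- Apply the same order in the TNF subgroups, and report which structure each model used.

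The cost is a few lines of SAP text and code. There are two limits. Sandwich errors are slightly liberal in small subgroups, which is why they come last. They also correct only the variance: under missing-at-random dropout, on which SAP 2.7.3 relies, a misspecified covariance can still bias the estimate. The SAP's latest revision, dated 08-Jul-2021, is recorded as made after database lock, so a change now must be documented as a post-lock change. At a minimum, the report should state whether any MMRM reached the fallback.

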#### **5.4.5 Exposure-adjusted incidence rate and $100*(1-\alpha)\%$ confidence interval**

It will be assumed that for each of  $n$  subjects in a clinical trial the time  $t_j$  ( $j=1, \dots, n$ ) to the first occurrence of a certain event is observed, or if the event was not experienced, the (censored) time to the end of the observation period. The total exposure time will be the total number of days with an actual dose greater than zero summed up over all patients, and then divided by 365.25 days. Incidence rate will be calculated per 100 patient years.

The sequence of first occurrences of an event will be modeled to follow approximately a Poisson process with constant intensity  $\theta$ . The rate parameter  $\theta$  will be estimated as  $\lambda = D/T$ , where  $T = \sum t_j$ , ( $j=1, \dots, n$ ) and  $D$  is the number of subjects with at least one event. Conditionally on  $T$ , an exact  $100*(1 - \alpha)\%$  confidence interval for a Poisson variable with parameter  $\theta T$  and observed value  $D$  can be obtained based on (Garwood,1936), from which an exact  $100*(1 - \alpha)\%$  confidence interval for  $D/T$  will be derived as follows (Sahai and Anwer, 1993; Ulm, 1990):

Lower confidence limit:

$$L = \frac{0.5c_{\alpha/2, 2D}}{T} \text{ for } D > 0, 0 \text{ otherwise,}$$

Upper confidence limit :

$$U = \frac{0.5c_{1-\alpha/2, 2D+2}}{T}$$

where  $c_{\alpha, k}$  is the  $\alpha$  th quantile of the Chi-square distribution with  $k$  degrees of freedom.

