## **2.4 Treatments (study treatment, rescue medication, concomitant therapies, compliance)**

### **2.4.1 Study treatment / compliance**

#### **Study Treatment**

The summaries by treatment group will be performed by the actual treatment received (as follows) for every visit until Week 16.

Treatment groups in Treatment Period 1:

- Secukinumab 150 mg

In Treatment Period 2, the summaries by treatment group will be performed by the actual treatment received (as follows) for every visit up to Week 52, including patients who switched at Weeks 16.

Treatment groups in Treatment Period 2:

- Secukinumab 150 mg - 300 mg (IR)
- Secukinumab 150 mg - 150 mg (IR)
- Secukinumab 150 mg – 150 mg (R)

where, R: Responders and IR: Inadequate Responders

Treatment groups in entire treatment period:

- Secukinumab 150 mg

- Secukinumab 300 mg

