### **Duration of exposure**

The duration of exposure (in days) will be summarized by means of descriptive statistics for the Enrolled Set, the Responder Set, and each treatment group for the Safety Set. In addition, the number of subjects with exposure of at least certain time thresholds will be displayed (e.g. any exposure,  $\geq 1$  week,  $\geq 2$  weeks,  $\geq 3$  weeks,  $\geq 4$  weeks,  $\geq 8$  weeks, etc.).

For Treatment Period 1, the end date for the calculation of duration of exposure will be the earlier of:

- Date of last injection in Treatment Period 1 + 84 days, and
- Date of first injection in Treatment Period 2

For Treatment Period 2, the end date for the calculation of duration of exposure will be the date of last injection in Treatment Period 2 + 84 days.

For entire treatment period, the end date for the calculation of duration of exposure will be the date of last injection + 84 days.

For patients with death as an event, end date for calculation of duration of exposure will be the date of death if it is earlier than the date of last injection + 84 days.

Duration of exposure (years) = duration of exposure (days) / 365.25

Duration of exposure (100 patient years) = duration of exposure (years) / 100

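### SAP 5.4.5 gives two incompatible denominators for the exposure-adjusted AE rate; the one in words counts injection days rather than time at risk

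*SAP*

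**What the plan says.** SAP 2.8.1 plans exposure-adjusted incidence rates with 95% confidence intervals for the entire treatment period, in tables and in graphs by system organ class. The columns are the pooled 150 mg and 300 mg groups listed in SAP 2.4.1 under "Treatment groups in entire treatment period". Patients who move from 150 mg to 300 mg appear in both.

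SAP 5.4.5 describes the denominator in two ways:

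- **In words:** "The total exposure time will be the total number of days with an actual dose greater than zero summed up over all patients", then divided by 365.25.
- **In the formula:** the rate is D/T. D "is the number of subjects with at least one event". T is the sum of t_j, where t_j is the time to a patient's first event, "or if the event was not experienced, the (censored) time to the end of the observation period". Both confidence limits use this T.

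SAP 2.4.1 treats exposure as continuous time. "For entire treatment period, the end date for the calculation of duration of exposure will be the date of last injection + 84 days"; for a patient who dies, it "will be the date of death if it is earlier than the date of last injection + 84 days". It converts the result to the unit of the rate: "Duration of exposure (100 patient years) = duration of exposure (years) / 100". For Treatment Period 1 only, exposure is cut at the "Date of first injection in Treatment Period 2" if that comes first.

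**The concern.** Each injection acts for weeks, so a count of injection days does not measure how long a patient was at risk. The sentence nevertheless reads as a programming instruction, and it is the only text in 5.4.5 that gives the conversion to years. SAP 2.1.1 also defines treatment start and end as dates on which a non-zero dose was given, which makes the literal reading a natural one.

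The error would also differ between columns. The weekly loading doses all fall in 150 mg time, so that column has more injection days per day of follow-up than the 300 mg column. A rate meant to correct for unequal exposure would then create an apparent excess on 300 mg.

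A second gap concerns switchers. The cut at the first Period 2 injection is stated for Period 1 exposure and for the period-specific treatment-emergent definitions. It is not stated for the pooled table, where the only end date is last injection + 84 days.

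**Working it through.** **Inputs**
- Injection days: 7 in Period 1 (baseline and Weeks 1, 2, 3, 4, 8, 12) and 9 in Period 2 (Weeks 16 to 48, every 4 weeks), from Protocol 5.2.
- Follow-up: Period 1 is 112 days. Period 2 is 252 days to Week 52, or 32 × 7 + 84 = 308 days to last dose + 84.
- Patient flow (SAP 3): 270 enrolled; 10% stop in Period 1; of the rest 10% are responders, 80% inadequate responders, 10% non-responders.
- Assumption: no Period 2 dropout, because the documents give no rate.

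**Plan's own figure.** 270 × 0.90 × 0.80 = 194.4, matching the stated 194. That is 97.2 per arm, with 24.3 responders and 24.3 non-responders among the 243 who complete Period 1.

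**Injection-day denominators**
- 150 mg: 243 × 7 + (97.2 + 24.3) × 9 = 2,794.5 days = 7.65 patient-years (PY).
- 300 mg: 97.2 × 9 = 874.8 days = 2.40 PY.

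**Time at risk**
- 150 mg to Week 52: 243 × 112 + 121.5 × 252 = 57,834 days = 158.3 PY.
- 300 mg to Week 52: 97.2 × 252 = 24,494 days = 67.1 PY.
- 150 mg to + 84 days, switchers cut at Week 16: 97.2 × 112 + 121.5 × 420 + 24.3 × 168 = 65,999 days = 180.7 PY.
- 300 mg to + 84 days: 97.2 × 308 = 29,938 days = 82.0 PY.

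**Inflation.** For uncommon events the sum of t_j is close to total follow-up, so inflation is follow-up days divided by injection days. At equal true rates, the false ratio is the 300 mg inflation divided by the 150 mg inflation.

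| Follow-up to | 150 mg | 300 mg | False 300/150 ratio |
|---|---|---|---|
| Week 52 | 20.7-fold | 28.0-fold | 1.35 |
| Last dose + 84 days | 23.6-fold | 34.2-fold | 1.45 |

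**Sensitivity** (ratio to Week 52; ratio to + 84 days)
- Adding the 27 planned Period 1 discontinuers, all stopping after the same dose (1 to 7): 1.35 to 1.38; 1.41 to 1.45.
- Instead assuming 10 to 20% Period 2 dropout, spread evenly over stopping after doses 1 to 8: 1.36 to 1.37; 1.47 to 1.49.
- Both together, with all Period 2 dropouts stopping after the same dose as the extreme: 1.35 to 1.42; 1.41 to 1.53.
- A common event, true rate 50 per 100 PY, constant hazard, T stopped at first event, no dropout: 17- and 24-fold to Week 52 (ratio 1.40); 19- and 28-fold to + 84 days (ratio 1.49).

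**Example.** Five patients with an event on 300 mg, using the section's exact limits, 0.5 × χ²(0.025; 10)/T and 0.5 × χ²(0.975; 12)/T:
- T = 81.96 PY (full follow-up as an approximation): 6.1 per 100 PY (95% CI 2.0 to 14.2).
- T = 2.395 PY (injection days): 209 per 100 PY (68 to 487).

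**Switcher overlap.** If a switcher's 150 mg time ran to the last 150 mg dose + 84 days, it would end at Week 24, which is 56 days past Week 16. Then 97.2 × 56 = 5,443 days = 14.9 PY would count in both columns, and 14.9/180.7 = 8% of the 150 mg column.

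**The case against.** The estimator as printed is correct. Section 5.4.5 defines t_j, sets T to its sum and uses T in the rate and both limits, while the total in the disputed sentence enters no formula. The exposure rules in SAP 2.4.1, the + 84-day window in 2.8.1 and the 52-week on-treatment period in 2.1.1 all point to continuous time. A programmer who follows any of them produces no error of this kind.

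The reach is also limited. The pooled columns are not a randomised comparison, and no rate ratio is planned. Both randomised arms have 9 injection days over the same Period 2 time, and crude incidence does not use the denominator. An error this large might well be noticed: five patients out of 97 shown as 209 per 100 PY would look odd beside the crude incidence, and the 2.4.1 exposure table would show about 181 PY for 150 mg against 7.7.

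All of this stands, and it makes the consequence conditional. It does not remove the contradiction, because the SAP ranks neither definition above the other. The overall inflation would be easier to spot than the 35 to 45% difference between columns. The switcher overlap rests on a reading that the SAP does not state for the pooled table; the gap there is a missing cross-reference.

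**Conclusion.** The concern holds. SAP 5.4.5 contains a denominator that is wrong for an intermittently injected drug and conflicts with its own formula and with 2.4.1. If the sentence were coded, pooled entire-period rates for uncommon events would be about 21 to 34 times too high. Equal true rates would show a 300/150 ratio of about 1.35 to 1.45. Those values span two follow-up conventions and rest on the planned patient flow without Period 2 dropout. Assumed dropout widens the ratio to at most 1.53, and commoner events are inflated less. With T as in the formula, there is no inflation and the expected ratio is 1. The affected outputs are the entire-period exposure-adjusted tables and the graphs by system organ class that show the same rate. Efficacy results are not involved.

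**What to change.** Amend SAP 5.4.5:

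1. Delete the sentence on days with a dose above zero. State that total exposure is the sum of t_j divided by 365.25, with t_j running to the first event or otherwise to the end of the SAP's existing window (last dose + 84 days, or death if earlier), by reference to 2.4.1 and 2.8.1.
2. State that in the pooled table a switcher's 150 mg time ends at the first Period 2 injection, as 2.4.1 already does for Period 1, and that each event counts under the dose at onset.
3. Note one limitation. A completer's last visit is at Week 52, 28 days after the last dose, so the final 56 days of the window are not fully observed. Under Protocol 7.1 and 7.2.1.1, all SAEs are reported for 30 days after the last visit and later ones only if suspected to be related. New non-serious events thought to be related go into source documents only. If no event were captured in those 56 days, a completer's rate would be lower than with time to Week 52 by 1 − 364/420 = 13% on 150 mg throughout and by 1 − 252/308 = 18% for the 300 mg phase.

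The cost is wording only: one sentence removed, one cross-reference and one note, with no new data or table. The latest SAP version is already after database lock, so this should be a dated clarification.
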